5.4 Impact of non-compliance with study treatment

Based on the observed differences in cholesterol during follow-up between all those allocated active anacetrapib and all those allocated placebo (i.e. irrespective of compliance), cholesterol-weighted analyses will be used to estimate the effects of actual compliance with anacetrapib on the primary and secondary outcomes overall and in different circumstances.⁶ The effect of full compliance with anacetrapib will also be estimated based on the observed intention-to-treat effects on the primary and secondary outcomes of allocation to anacetrapib and the average in-trial compliance with the randomized treatment (determined by participant reports and treatment issue records).

5.5 Analysis of safety and biochemical outcomes

For each of the events listed as additional safety outcomes (section 4.5), the number of randomized participants with at least 1 event will be compared using standard tests for differences in proportions. For analyses of continuous variables, differences in means between the randomized groups will be assessed (unless otherwise specified). Exploratory analyses will be conducted among particular categories of participant. For participants selected for blood sampling who were alive at the time of the scheduled follow-up assessment but failed to provide a sample, LDL- and HDL-cholesterol values will be imputed based on baseline and 2 month values while taking into account their background atorvastatin and reported compliance.

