4.4 Tertiary assessments

Tertiary assessments will involve intention-to-treat analyses among all randomized participants of the effects of allocation to anacetrapib versus placebo during the scheduled treatment period on:

- (i) Coronary death or myocardial infarction, and, separately, myocardial infarction alone
- (ii) Mortality
 - from all causes combined; and, separately, within particular categories of causes, i.e.:
 - all cardiovascular causes combined; and, separately:
 - coronary (including sudden cardiac death)
 - other cardiac
 - stroke
 - other vascular
 - all non-cardiovascular causes combined; and, separately:
 - cancer
 - infection
 - respiratory
 - hepatic
 - other medical*
 - non-medical

* including undetermined cause

- (iii) Stroke
 - of any type combined; and, separately, of particular types, i.e.:
 - confirmed ischaemic stroke
 - confirmed haemorrhagic stroke
 - stroke of unknown/unconfirmed aetiology
- (iv) Major coronary events, major atherosclerotic events, and major vascular events, separately, in various subdivisions:
 - (a) occurring more than one year after randomization;
 - (b) disease type prior to randomization:
 - coronary heart disease
 - cerebrovascular disease

REVEAL Data Analysis Plan

- peripheral arterial disease
- diabetes*

and timing of most recent qualifying vascular event: <12; ≥12 months

* diabetes at randomization is defined as self-reported diabetes recorded on screening or randomization form; or diabetes-related adverse event recorded on or before date of randomization; or use of hypoglycaemic medication reported on randomization form

(c) three similar-sized groups based on lipid and lipoprotein measurements* from the Randomization visit:

- HDL cholesterol (mmol/L): <0.9; ≥0.9<1.1; ≥1.1
- LDL cholesterol (mmol/L): <1.4; ≥1.4<1.7; ≥1.7
- total cholesterol (mmol/L): <3.2; ≥3.2<3.7; ≥3.7
- non-HDL cholesterol (mmol/L): <2.2; ≥2.2<2.6; ≥2.6
- triglycerides (mmol/L): <1.2; ≥1.2<1.7; ≥1.7
- apolipoprotein B (mg/dL): <60; ≥60<70; ≥70
- apolipoprotein A1 (mg/dL) <110; ≥110<125; ≥125
- lipoprotein (a) (nmol/L): <15; ≥15<55; ≥55

* using results measured in the central laboratory

(d) various other categories of participant based on their Randomization visit values:

- age (years): <65; ≥65<70; ≥70
- sex: male; female
- region: North America; Europe; Asia
- blood pressure (mmHg):
 - systolic <125; ≥125<140; ≥140
 - diastolic <75; ≥75<85; ≥85
- kidney function

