4.5 Additional safety assessments

Additional safety assessments will include intention-to-treat analyses among all randomized participants of the effects of allocation to anacetrapib versus placebo during the scheduled treatment period on:

- (i) blood pressure-related outcomes:
 - blood pressure at 12 months and at final follow-up visit
 - mean level of systolic blood pressure (SBP) and diastolic blood pressure (DBP)
 - level of SBP (<140; ≥140<160; ≥160<180; ≥180 mmHg) and level of DBP (<90; ≥90<100; ≥100<110; ≥110 mmHg)
 - change from randomization in SBP and DBP (in each case <-10; ≥-10<0; ≥0<10; ≥10 mmHg)
 - serious adverse events due to hypertension
- (ii) muscle-related outcomes:

REVEAL Data Analysis Plan

- creatine kinase [CK] >5x and ≤10x laboratory upper limit of normal [ULN] plus ALT >1.5x ULN
- CK >10x and ≤40x ULN overall and, separately, with muscle symptoms
- CK >40x ULN overall and, separately, with evidence of end-organ damage, such as doubling of serum creatinine (i.e. rhabdomyolysis[°])

(iii) liver-related outcomes:

- ALT >3x ULN plus bilirubin >2x ULN, with CK ≤5x ULN
- ALT >3x ULN on 2 occasions within about one week (i.e. 1 to 14 days), with CK ≤5x ULN
- liver injury (i.e. ALT >3x ULN plus bilirubin >2x ULN; ALT >10x ULN [regardless of bilirubin level]; liver transplantation; or death due to liver disease) by cause*

* causes to be classified as: known (e.g. infection; alcohol; cancer; drug-related [excluding randomized anacetrapib/placebo]); and unknown (including cases believed due to study treatment with no alternative cause identified)

(iv) renal function at final visit

- estimated glomerular filtration rate (eGFR)
 - difference in mean eGFR
 - development of impaired renal function (i.e. eGFR <60ml/min/1.73m²) among those with normal renal function (i.e. eGFR ≥60ml/min/1.73m²) at randomization.
- albuminuria
 - development of albuminuria (urinary albumin:creatinine ratio [uACR] ≥3 mg/mmol) in those with normo-albuminuria at randomization
 - development of macro-albuminuria in those with normo- or micro-albuminuria at randomization.

(v) discontinuation of study treatment* overall and, separately, by various causes

- serious adverse events**
- non-serious adverse events**
- other reasons (various categories; e.g. cannot attend clinic, participant concern, medical advice, administrative reason)

* reason recorded at time of latest discontinuation (without any subsequent restart)

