4.6 Analyses of biochemical efficacy

Biochemical efficacy of anacetrapib 100 mg daily will be assessed in non-fasting specimens taken from all participants at the randomization visit, at the 2 month follow-up visit, at a follow-up visit when median follow-up is about 2 years and at the final study visit. In addition, samples will be taken annually in 5% of participants. The following biochemical efficacy outcomes will be measured using standard automated assays on all samples:

- total cholesterol
- HDL cholesterol
- LDL cholesterol
- non-HDL cholesterol
- triglycerides
- apolipoprotein A1
- apolipoprotein B

In addition, lipoprotein (a) is to be measured in all participants at randomization and at about 2 years after the median participant is randomized, and in at least 5% of participants annually.

[°] For the purposes of these analyses, rhabdomyolysis is defined as CK>40x ULN with muscle symptoms or CK>10x ULN with evidence of end-organ damage such as doubling of serum creatinine

Samples of genetic material, plasma, serum, and urine have been biobanked for possible future analyses.

The effect of anacetrapib on other aspects of lipid and lipoprotein profile (such as lipoprotein particle size) may also be examined. In particular, a sub-study is comparing the assessment of LDL cholesterol using a direct method (which is used routinely for REVEAL samples) with a beta quantification method among around 2000 samples taken at 2 years of follow-up. The results of this sub-study may inform the interpretation of the main analyses of the effect of anacetrapib on LDL cholesterol concentration.

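### Continuous safety and lipid outcomes are compared by differences in means with no baseline adjustment named, although randomization values exist: a minor loss of precision

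*SAP*

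**What the plan says.** Section 5.5 of the SAP sets the method for all continuous safety and biochemical outcomes in one sentence: "For analyses of continuous variables, differences in means between the randomized groups will be assessed (unless otherwise specified". No other section specifies a different model for them.

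The outcomes concerned are:
- **Blood pressure** (section 4.5(i)): "mean level of systolic blood pressure (SBP) and diastolic blood pressure (DBP"), at 12 months and at the final visit.
- **Renal function** (section 4.5(iv)): "difference in mean eGFR" at the final visit.
- **Lipids** (section 4.6). Biochemical efficacy "will be assessed in non-fasting specimens taken from all participants at the randomization visit", and again in everyone at 2 months, at about 2 years and at the final visit. In addition, "samples will be taken annually in 5% of participants".

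Randomization values therefore exist for all three. The SAP uses them for subgroups (section 4.4(iv)), for categories of blood pressure change and at-risk renal subsets (section 4.5), and for filling in missing lipids (section 5.5): "LDL- and HDL-cholesterol values will be imputed based on baseline and 2 month values". It does not use them to adjust a difference in means. Section 5.5 also announces analyses in smaller sets of participants: "Exploratory analyses will be conducted among particular categories of participant".

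**The concern.** A follow-up mean can be compared between arms without adjustment, as a change from baseline, or adjusted for baseline by analysis of covariance (ANCOVA). All three are differences in means, and section 5.5 does not say which is intended. Its plain reading is the unadjusted one, which discards information already collected. The plan itself treats baseline as predictive of follow-up, since it imputes missing LDL and HDL cholesterol partly from it.

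Under randomization the unadjusted difference is unbiased and its type I error is correct. What is at stake is the width of the confidence intervals, and this can matter in practice only where numbers are small: the 5% annual lipid samples and the analyses in particular categories of participant.

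**Working it through.** The SAP states no SD, detectable difference or power for a continuous outcome, so there is no planned figure to reproduce.

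**Inputs from the SAP**
- Over 30,000 randomized (section 2.1); 30,000 used.
- 28,613 surviving participants in May 2016 (section 5.1). Half of this, 14,306 per arm, is used for the full-size case. It is an upper bound, because it treats every survivor as measured.
- Annual lipid samples in 5% (section 4.6): 0.05 × 30,000 = 1,500, or 750 per arm.
- Two-sided 5% significance (section 5.1).
- LDL cholesterol cut-points 1.4 and 1.7 mmol/L, dividing participants into "three similar-sized groups based on lipid and lipoprotein measurements" (section 4.4(iv)(c)).

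**Assumptions**
- Allocation is 1:1.
- ρ, the correlation of baseline with follow-up, is 0.3 to 0.8.
- The SD and the baseline slope are the same in both arms.
- SBP has an SD of 18 mmHg.

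**Formulas**
- SE = SD × √(2/n) × √(1−ρ²), with n per arm; ρ = 0 gives the unadjusted comparison.
- 95% CI half-width = 1.96 × SE.
- Power = Φ(d/SE − 1.96) for a true difference d.

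**Reduction in SE.** √(1−ρ²) is 0.954, 0.866, 0.714 and 0.600 at ρ = 0.3, 0.5, 0.7 and 0.8, so the SE falls by 5%, 13%, 29% and 40%. This proportion is the same at every sample size.

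**5% annual samples, 750 per arm** (unadjusted SE = √(2/750) = 0.0516 SD)

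| ρ | SE (SD) | Half-width (SD) | Power, 0.10 SD | Power, 0.15 SD | Power, 0.20 SD |
|---|---|---|---|---|---|
| 0 (unadjusted) | 0.0516 | 0.101 | 49% | 83% | 97% |
| 0.3 | 0.0493 | 0.097 | 53% | 86% | 98% |
| 0.5 | 0.0447 | 0.088 | 61% | 92% | 99% |
| 0.7 | 0.0369 | 0.072 | 77% | 98% | about 100% |

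At ρ = 0.5, adjustment makes 750 per arm worth 750/0.75 = 1,000. Taking 5% of 28,613 instead (715 per arm) changes little: the half-width is 0.104 SD unadjusted and 0.090 SD at ρ = 0.5.

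**In LDL units.** If randomization LDL is roughly normal, the tertile points lie 0.4307 SD either side of the mean, so SD = (1.7 − 1.4)/(2 × 0.4307) = 0.348 mmol/L. If each cut-point is rounded by up to 0.05, the range is 0.232 to 0.464. With 0.348, the half-width at 750 per arm is 1.96 × 0.348 × 0.0516 = 0.035 mmol/L unadjusted, about 0.030 at ρ = 0.5 and 0.025 at ρ = 0.7. This carries the randomization SD over to follow-up values on treatment, which is a further assumption.

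**Full size, 14,306 per arm.** Unadjusted SE = √(2/14,306) = 0.0118 SD. Power for 0.05 SD is 98.8% unadjusted and 99.8% at ρ = 0.5. The SBP half-width is 1.96 × 18 × 0.0118 = 0.42 mmHg, against 0.36 mmHg at ρ = 0.5.

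**A category holding 10% of participants** (an illustrative size; about 1,430 per arm). Power for 0.1 SD is 76% unadjusted, 87% at ρ = 0.5 and 96% at ρ = 0.7. In one of the lipid thirds (14,306/3, about 4,770 per arm), unadjusted power for 0.1 SD is already about 99.8%.

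**The case against.** The strongest reply is that nothing here is an error. The unadjusted comparison is valid, the SAP's wording allows for exceptions and does not rule out an adjusted difference, and imputing missing lipids from baseline does not oblige anyone to adjust the group comparison. Most of these outcomes are also measured in everyone, so precision is ample: blood pressure and eGFR are not tied to the 5% sample, and lipids are measured in all participants at three follow-up times. No decision rule or multiplicity step depends on the annual samples. The power gap quoted at 0.1 SD is about 0.035 mmol/L of LDL, and nothing in the SAP suggests that so small a shift matters. Finally, ρ is assumed, and at 0.3 the gain in the 5% sample is only 49% to 53%.

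Much of this stands. It rules out bias, limits the practical effect to small samples and small differences, and keeps the point minor. It does not show that the plan is better as written. If the sentence means an unadjusted comparison, it gives up precision without any return. If it permits adjustment, the choice between estimators is left open. One sentence settles both.

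**Conclusion.** The point holds and is minor. The only method stated for continuous outcomes is a difference in means, no baseline covariate is named, and randomization values exist for lipids, blood pressure and eGFR. The consequence is wider confidence intervals than necessary, with no bias and no effect on the primary or secondary event outcomes.

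At full size the loss is negligible. It becomes noticeable only in the 5% annual samples, for differences below about 0.2 SD, and in small participant categories. These sizes rest on the assumed ρ, 1:1 allocation and a common SD and slope in both arms. The point is not extended to the mood and cognitive scores in section 4.7, because the SAP does not say whether they have randomization values.

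**What to change.** Add to section 5.5 wording such as:

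> Where a variable was measured at randomization, its follow-up means will be compared by linear regression on allocated treatment with the randomization value of that variable as a covariate (ANCOVA), reported with 95% confidence intervals. A missing randomization value will be replaced by the overall mean, calculated without regard to allocation, so that no randomized participant with a follow-up value is excluded.

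Keep the unadjusted difference as a supporting analysis. The rule for missing values has to be stated here because the one in section 5.3 only assigns participants to subgroups.

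The cost is a short addition to the SAP and a little more analysis work. No new data are needed, and the quantity estimated is still the mean difference between the arms.

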5.1 Methods of analysis

All participants randomized to anacetrapib will be compared with all participants randomized to placebo, regardless of whether a participant received all, some or none of their allocated treatment (i.e. intention-to-treat [ITT] analyses).^{2,3} A participant may contribute to more than one assessment if they have events of more than one type (e.g. non-fatal ischaemic stroke followed by coronary death). For the time-to-event analyses, survival analytic methods will be used to evaluate the time to the first event during the entire study period. For each outcome, log-rank method will be used to estimate the average event rate ratio comparing all those allocated active anacetrapib with all those allocated placebo.³ Estimates of the event rate ratio will be shown with 95% confidence intervals. Kaplan-Meier estimates for the time to each of the primary and secondary outcomes will also be plotted (with their associated log-rank p-values). Cox regression may be used where rate ratios are extreme (e.g. > 2 or < 0.5). In all analyses, two-sided p-values (2P) < 0.05 will be considered statistically significant (after any allowance for multiplicity as outlined in section 5.2).

Recurrent events will be analysed using the negative binomial and sensitivity analyses will be performed using alternative methods such as the Andersen-Gill approach.

At the time of finalizing the Data Analysis Plan in May 2016, around 99% of the 28,613 surviving randomized participants had attended their most recent scheduled visit. Since loss-to-follow-up at study end is anticipated to be minimal (<1%), no exploratory analyses investigating the impact of missing data not at random/informative missingness are planned.

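### Does imputing missed blood samples for LDL- and HDL-cholesterol only leave the other six lipid outcomes wrongly specified?

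*SAP*

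**What the plan says.** Section 4.6 names seven assays, introduced by "The following biochemical efficacy outcomes will be measured using standard automated assays on all samples": total, HDL, LDL and non-HDL cholesterol, triglycerides, and apolipoproteins A1 and B. Samples are due from everyone at randomization, "at the 2 month follow-up visit, at a follow-up visit when median follow-up is about 2 years and at the final study visit", with annual samples in 5% of participants. Lipoprotein (a) is the eighth outcome, on its own schedule: "lipoprotein (a) is to be measured in all participants at randomization and at about 2 years after the median participant is randomized", and annually in at least 5%.

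Section 5.5 sets the analysis: "For analyses of continuous variables, differences in means between the randomized groups will be assessed". Its imputation rule applies to "participants selected for blood sampling who were alive at the time of the scheduled follow-up assessment but failed to provide a sample", and for them "LDL- and HDL-cholesterol values will be imputed based on baseline and 2 month values while taking into account their background atorvastatin and reported compliance". It names no other analyte.

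Section 5.1 sets the general principle: "All participants randomized to anacetrapib will be compared with all participants randomized to placebo". It also reports that, when the plan was finalized in May 2016, "around 99% of the 28,613 surviving randomized participants had attended their most recent scheduled visit".

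**The concern.** A single missed blood sample loses every analyte due at that visit, yet the rule restores only two. If the other six were then compared among sample-givers only, LDL- and HDL-cholesterol would describe all living participants selected for sampling, and the other six a subset of them. That sits awkwardly with the intention-to-treat principle in section 5.1. If people who have stopped treatment also tend to miss samples, the effect on, say, apolipoprotein B would be somewhat overstated as an effect of allocation.

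Three further details look loose:

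- The 2-month visit is both an input to the rule and a scheduled sampling visit, so read literally a missing 2-month value would be imputed from itself. Someone who missed both that sample and a later one lacks one of the inputs.
- The rule does not carry over directly to lipoprotein (a), which is not scheduled for all participants at 2 months.
- The SAP does not say whether imputation is single or multiple.

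At stake is the size of the reported effect on six biochemical outcomes and, if the unspecified cholesterol measure in section 5.4 is total or non-HDL cholesterol, an input to the cholesterol-weighted compliance analyses.

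**Working it through.** **Count.** Section 4.6 gives 7 + 1 = 8 lipid outcomes. Section 5.5 covers 2, leaving 8 - 2 = 6. The other missing-data statements do not reach them: section 5.3 places missing baseline values into subgroups, and section 5.1 deals with loss to follow-up.

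**Size of a sample-givers-only comparison.** The SAP states no figure to reproduce, so this is an illustration. Let m be the share of living, selected participants without a sample, and let s and n be the shares off treatment among givers and non-givers. Assume that the lipid effect is proportional to the share on treatment. The effect among givers relative to the effect among all is then

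R = (1 - s) / [(1 - m)(1 - s) + m(1 - n)].

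The SAP gives none of m, s or n. Take s = 0.10 throughout. The value m = 0.01 corresponds to the 99% attendance in section 5.1, although attending is not the same as giving blood. The values 0.05 and 0.10 have no source in the document.

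| m | n | R | Relative difference |
|---|---|---|---|
| 0.01 | 0.50 | 0.9 / (0.891 + 0.005) = 1.0045 | +0.4% |
| 0.01 | 0.80 | 0.9 / (0.891 + 0.002) = 1.0078 | +0.8% |
| 0.05 | 0.50 | 0.9 / (0.855 + 0.025) = 1.023 | +2.3% |
| 0.05 | 0.80 | 0.9 / (0.855 + 0.010) = 1.040 | +4.0% |
| 0.10 | 0.50 | 0.9 / (0.810 + 0.050) = 1.047 | +4.7% |
| 0.10 | 0.80 | 0.9 / (0.810 + 0.020) = 1.084 | +8.4% |
| any | 0.10 | 1.000 | 0 |
| 0.10 | 0.05 | 0.9 / (0.810 + 0.095) = 0.9945 | -0.6% |
| 0.10 | 0 | 0.9 / (0.810 + 0.100) = 0.9890 | -1.1% |

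At m = 0.01 the two analysis sets would differ by about 0.01 x 28,613 = 286 people.

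**Non-HDL cholesterol.** One might expect total minus imputed HDL-cholesterol to disagree with non-HDL cholesterol. If the six are analysed on observed samples, nobody with an imputed HDL value has an observed total or non-HDL value at that visit, and sample-givers have all three observed. No conflict can arise within a participant. At most, published means rest on slightly different denominators, which reporting the numbers analysed makes plain.

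**Missing 2-month value.** The rule bases imputation on baseline and 2-month values together with atorvastatin and reported compliance. It does not bar using whichever of these exist. At the 2-month visit itself the only workable reading is to use the remaining inputs.

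**What depends on it.** The testing sequence in section 5.2 concerns clinical events; none of the six lipid outcomes is in it. Section 5.4 is touched only if its cholesterol measure is one that is not imputed, and then by the percentages above.

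**The case for a change.** The case for amending is that the SAP chose to write an imputation rule and wrote it incompletely. By including reported compliance among the inputs, it treats compliance as relevant to the missing values, and that reasoning applies equally to apolipoprotein B or non-HDL cholesterol. Leaving the analysis set open for six of eight outcomes permits a choice after unblinding, and one or two sentences would close it.

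The textual part stands: six outcomes have no stated rule, the 2-month fallback is absent and the imputation method is not named. The step from there to a fault in the plan is weaker. The SAP never says that the six are to be analysed on sample-givers; that is an inference from its silence. Confining imputation to LDL- and HDL-cholesterol may be deliberate. The direction of any bias is not established, and the larger figures depend wholly on assumed missing and off-treatment rates. A single multiple-imputation model for all eight outcomes would go well beyond the gap, add dependence on the model, and bring no demonstrated gain if few samples are missing.

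**Conclusion.** No change is needed. Section 5.5 contains no false statement and no contradiction; it gives a rule for two outcomes and leaves routine detail open for the rest. Analysts would reasonably use available samples for the other six, report the numbers analysed, and impute LDL- and HDL-cholesterol from whatever inputs exist when the 2-month value is absent.

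If about 1% of samples are missing, the consequence is under 1% of the lipid effect in relative terms, and it could be zero or of opposite sign. That rests on three assumptions: missed samples are about as rare as missed visits, the effect is proportional to the share on treatment, and the off-treatment shares are as tabulated. If as many as 10% of samples were missing, mostly from people off treatment, the overstatement could reach 4.7-8.4%. The SAP gives no support for that rate, and even then no event comparison would be affected.
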